4 STUDY DESIGN

4.1 OVERALL DESIGN

This is a feasibility/pilot, prospective cohort study to determine how to implement and refine Outreach-ER intervention for a larger clinical study.

Aim 1

To assess the feasibility and acceptability of Outreach-ER. This aim will be accomplished by collecting detailed process data which will allow the assessment of registration, enrollment, retention, and adherence/fidelity to the program. This is an important step prior to moving forward with a larger trial. We will also utilize mixed methods approach, including semi-structured interviews and surveys to assess the acceptability and experience of participants.

Aim 2

To assess feasibility of collecting outcomes and explore the effectiveness of Outreach-ER. In care partners, we will evaluate the pre-post benefits of Outreach-ER to improve mood (Center for Epidemiologic Studies Depression Scale-10), reduce burden (Zarit Burden Interview-12), reduce stress (Perceived Stress Scale) and improve quality of life. We will describe and report healthcare utilization in PLWD, such as 30-day hospital readmissions and number of emergency room visits.

4.2 OVERVIEW – STUDY PROCEDURES/DATA COLLECTION

The cohort of PLWD will be identified through the Regions and Methodist Hospital administrative database/EPIC Clarity report following acute care. This research investigation will take place mostly virtual or in-home.

4.3 END-OF-STUDY DEFINITION

A participant is considered to have completed the study 3 months after completing the final study visit, or 3 months after the final study visit

5 STUDY POPULATION

5.1 INCLUSION CRITERIA

In order to be eligible to participate in this study, a dyad must meet all of the following criteria:

1. *PLWD with a recent Emergency department visit or admission at Regions Hospital or Methodist Hospital*

2. *Diagnosis of dementia based on ICD Codes in the medical record*
3. *Provides informed consent prior to participation*
4. *Must be able to read and speak English*
5. *PLWD Living at Home*
6. *Age >=18 years for PLWD and their care partner*

5.2 EXCLUSION CRITERIA

A dyad who meets any of the following criteria will be excluded from participation in this study:

1. *PLWD living in a nursing home/Long term care – Assisted living facility*
2. *Current involvement in another clinical research study/trial for care partners*
3. *PLWD MRN on the HP exclusion list*

5.3 LIFESTYLE CONSIDERATIONS

NA

5.4 SCREEN FAILURES

Pre-screening: All potential participants will undergo a pre-screening chart review and a phone or a video call to determine whether they meet the inclusion/exclusion criteria. Patients will be considered ineligible if they do not meet one or more of the inclusion/exclusion criteria during pre-screening. We will collect information on why participants are ineligible or decide not to move forward with the trial.

Screen failures are defined as participants who are considered eligible during the pre-screening, but it was subsequently determined that they do not meet one or more of the inclusion/exclusion criteria. We will collect information on why participants screen fail or decide not to move forward with the trial.

5.5 STRATEGIES FOR RECRUITMENT AND RETENTION

Recruitment: A recruitment letter and flyer will be sent out to patients identified as eligible. Within a few days after discharge (2 days to 2 weeks) research staff will reach out to patients and their caregivers via a phone call. If interested, the caregiver and patient will be provided with informed consent to review on their own time. A video or phone encounter will be arranged to provide additional details of the study and informed consent. Participating subjects will need to explain in their own words what the study entails. A virtual consent through REDcap or a mailed consent with witness will be obtained.

Remuneration: Participants will be provided gift cards totaling \$100 per dyad for completing certain visits of the research study.

5.6 PARTICIPANT WITHDRAWAL

5.6.1 REASONS FOR PARTICIPANT WITHDRAWAL

Participants are free to withdraw from participation in the study at any time upon request.

An investigator may withdraw a participant from the study if:

- Any medical condition, event or situation occurs such that continued participation in the study would not be in the best interest of the subject.
- The participant meets an exclusion criterion (either newly developed or not previously recognized) that precludes further study participation.
- Significant study procedure non-compliance
- Lost-to-follow up; unable to contact subject

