1.2 SCHEMA

2 INTRODUCTION

2.1 BACKGROUND & STUDY RATIONALE

Alzheimer's disease affects 6.2 million individuals in the United States and results in an annual cost of care of \$355 billion, including \$239 billion in Medicare and Medicaid payments combined ("2021 Alzheimer's disease facts and figures," 2021). People living with dementia (PLWD) often receive poorly coordinated and fragmented care that can lead to ineffective care and poor health outcomes, including trips to the emergency department and hospitalizations (Hirschman & Hodgson, 2018). Care for PLWD is demanding and stressful, as the needs of those with dementia are constantly evolving as their behavior and abilities change. Caregivers often experience mental health concerns such as anxiety and depression, poor physical health, compromised immune system, and emotional and social issues due to the demands and stress of caregiving (Elliott, Burgio, & DeCoster, 2010; Ferrara et al., 2008).

Multicomponent non-pharmacological psychosocial care interventions such as REACH (Resources for Enhancing Alzheimer's Caregiver Health), or NYUCI (NYU Caregiver Intervention) include more than one care technique or delivery method to foster support, expertise, information, or skills for caregivers to improve caregiver quality of life and health outcomes. These interventions usually include therapy and social support, education, supportive feedback, goal setting, and planning, as well as relaxation and physical exercises. These are offered as structured approaches to develop skills for problem solving, improving communication and improve relationships for caregivers and PLWD. These approaches have been recognized as high priority in the Alzheimer's research community to study the real-world effectiveness and implementation across different health care settings (Larson & Stroud, 2021). The multicomponent interventions such as REACH, NYUCI have been shown to reduce stress, improve depression, well-being of caregivers and delays nursing home placement of PLWD (OUT, 2018). Key challenges to these interventions include implementation, identifying & tailoring interventions to specific level of dementia and care partner support, and efficacy of caregiver-related interventions (Gaugler, Jutkowitz, & Gitlin, 2020; Hodgson & Gitlin, 2021). REACH-TX was effective in improving quality of life and decreasing caregiver burden when administered by a community agency, as there were

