5.6.2 HANDLING OF PARTICIPANT WITHDRAWALS

The reason for participant discontinuation or withdrawal from the study will be recorded on the relevant eCRF.

A participant will be considered lost to follow-up if he or she fails to attend any scheduled study visit and study staff are unable to contact the participant after at least 5 attempts.

The following actions must be taken if a participant fails to attend any required study visit:

- Study staff will attempt to contact the participant, reschedule the missed visit, counsel the participant on the importance of maintaining the assigned visit schedule and ascertain if the participant wishes to and/or should continue in the study.
- Before a participant is deemed lost to follow-up, the investigator or designee will make every effort to regain contact with the participant (where possible, telephone calls or e-mail – if no answer leave a voicemail on the first and last attempt). These contact attempts will be documented.
- Should the participant continue to be unreachable, he or she will be considered to have withdrawn from the study with a primary reason of lost to follow-up.

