8.2.4 TIME PERIOD AND FREQUENCY FOR EVENT ASSESSMENT AND FOLLOW-UP

Upon consenting, a subject is considered to be a participant in the study, and until that person either withdraws or completes study, AEs and SAEs will be recorded. The investigational team will promptly report any AE/SAE as required per federal guidelines.

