9 STATISTICAL CONSIDERATIONS

9.1 STATISTICAL ANALYSIS PLAN

Aim 1: To assess the feasibility, acceptability, and fidelity of implementation of the Outreach-ER program we will begin by measuring the absolute number of potential care dyads of care partners (CP) and PLWD contacted for recruitment and the number of those who consent and enroll. These will be used to calculate the overall rate of program registration. The feasibility of collecting CP provided data will be evaluated by quantifying the missingness in the registration materials as well the response rate to the two questionnaires. Fidelity of the intervention will be assessed by describing CP attendance rates, length of intervention, and number of sessions as recorded by Outreach-ER staff. Completion patterns will be summarized overall and stratified by patient demographics. Any differences in intervention fidelity associated with CP and PLWD demographics will be described and discussed. Acceptability of the intervention will be assessed using data gathered through the post-intervention interview. The interviews will be transcribed, and recurring themes will be identified by the study team. If a participant withdraws before completion of the intervention this data will be solicited via telephone contact. Table 1 gives an example of how counts will be utilized throughout Aim 1 to describe the recruitment, enrollment, and adherence.

Table 2.

	Counts for feasibility	Use in analysis
Participants contacted	N	Total number of attempted recruits
Participants who enroll and consent	a	Recruitment rate: a/N
Participants who start Outreach-ER programming	b	Participation rate: b/N, compare to a/N
Participants who complete intervention (7+ visits)	c	Completion rate: c/b, used as main progression criteria Overall successful enrollment rate: c/N
Number who complete each intervention visit – k = 1, ..., 7	dk	Session specific completion rate: dk/b
Number who complete each questionnaire – m = 1,2	em	Questionnaire specific response rate: em/a and/or em/b if a ≠ b

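### A move to a care facility after enrolment can end a dyad's study follow-up, so the paired pre-post analysis may lose dyads selectively

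*Combined protocol and SAP*

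**What the plan says.** Section 5.2 excludes a dyad on the ground "PLWD living in a nursing home/Long term care – Assisted living facility". Section 5.6.1 opens its list of investigator-initiated withdrawals with "An investigator may withdraw a participant from the study if", and one item on that list is "The participant meets an exclusion criterion (either newly developed or not previously recognized) that precludes further study participation". The withdrawal is from the study, not only from the sessions.

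Section 2.1 says that comparable multicomponent programs reduce caregiver stress and that their use "delays nursing home placement of PLWD".

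On what follows a withdrawal:

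- Section 5.6.2 requires that "The reason for participant discontinuation or withdrawal from the study will be recorded on the relevant eCRF". It does not say which data are still collected.
- Section 8.2.4 sets the safety window: "until that person either withdraws or completes study, AEs and SAEs will be recorded".
- Section 9.1 (Aim 1) adds "If a participant withdraws before completion of the intervention this data will be solicited via telephone contact". In context, the data meant are those of the post-intervention interview, used for acceptability.
- Section 9.1 (Aim 2) computes CES-D-10, ZBI-12 and PSS totals from completed questionnaires and compares pre with post by paired t-tests. It gives no method for missing scores. Its one sensitivity analysis drops those who did not complete the intervention.
- Section 9.1 takes utilization counts from the EHR and does not say what happens to them after withdrawal.

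**The concern.** Facility residence is a sensible entry criterion for a home-based program. Once a dyad is enrolled, placement becomes something that happens to the person living with dementia during the study, and the protocol's own rationale links it to what such programs aim to change. A rule that allows this event to end study participation allows missing data to depend on outcome.

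Three things are at stake. The pre-post change on the care-partner scales would rest on dyads that were not placed. Adverse events after withdrawal, including hospitalizations (serious by definition in section 8.2.2), need not be recorded. The second-questionnaire response rate, a feasibility endpoint, would count an investigator's withdrawal as if the care partner had not responded. Because the pilot is meant to shape a larger study, the same rule could be carried forward.

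**Working it through.** **1. The chain in the text.** Facility residence is an exclusion (5.2). A newly developed exclusion is a ground for withdrawal from the study (5.6.1). Withdrawal closes AE/SAE recording (8.2.4). The only data explicitly sought after early withdrawal are the interview data (9.1). A paired test needs both questionnaires, so a dyad without the second drops out of it. Each link is stated, except that the absence of later scales rests on silence.

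**2. The plan's own figures.** Section 9.2 gives detectable CES-D-10 changes at 80% power and two-sided alpha 0.05. Solving the paired t-test with the noncentral t distribution gives:

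| SD | N = 30, plan | N = 30, recomputed | N = 24, plan | N = 24, recomputed |
|---|---|---|---|---|
| 2 | 1.1 | 1.06 | 1.2 | 1.19 |
| 4 | 2.1 | 2.12 | 2.4 | 2.39 |
| 6 | 3.2 | 3.18 | 3.6 | 3.58 |

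All six entries are reproduced. The table treats 20% dropout as a smaller N. That covers lost precision; it does not cover a shift caused by who is lost.

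**3. Possible shift on a scale (assumed inputs).** Let k of 30 dyads be lost, and let their mean change differ from that of the retained dyads by g points. The retained mean then differs from the all-enrolled mean by (k/30) × g.

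| k | g = 2 | g = 4 | g = 8 |
|---|---|---|---|
| 1 | 0.07 | 0.13 | 0.27 |
| 2 | 0.13 | 0.27 | 0.53 |
| 3 | 0.20 | 0.40 | 0.80 |
| 6 | 0.40 | 0.80 | 1.60 |

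The sign follows g. If the lost dyads did worse, the reported change looks better; if they did better, it looks worse; if g = 0, there is no shift.

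For scale, take a true overall change of 0, SD 4 among the retained, and lost dyads who did worse by 4 to 8 points. The retained mean is then −(k/30) × g, with 30 − k − 1 degrees of freedom and noncentrality (k/30) × g / 4 × √(30 − k). The chance of a significant apparent benefit is 7% to 17% for k = 3 and 15% to 47% for k = 6, against a nominal 2.5% in that direction. With g reversed, the same probabilities apply to an apparent harm. The case k = 6 uses up the plan's whole 20% dropout scenario (6/30) on placement alone, so it is an upper illustration.

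**4. Utilization (assumed inputs, and only if EHR extraction stopped at withdrawal, which the plan does not say).** Suppose retained dyads average 0.5 acute visits and 3 of 30 are placed.

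- Placed average 2: (27 × 0.5 + 3 × 2)/30 = 0.65, against 0.50 reported; 0.15/0.65 = 23% too low.
- Placed average 0.5: 0.50, no bias.
- Placed average 0.2: (27 × 0.5 + 3 × 0.2)/30 = 0.47, against 0.50 reported; the error has the opposite sign.

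**5. Feasibility rates.** The main progression criterion is c/b, completers over starters. If 30 start, 3 are withdrawn before completing and the rest complete, c/b = 27/30 = 90%. The withdrawn dyads stay in the denominator, so the rate is not inflated. The second-questionnaire rate would also be 27/30 = 90%, with the three withdrawals indistinguishable from non-response.

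**The case against.** The strongest reply is that this is a silence in a small pilot and not a demonstrated loss. Several parts of it stand.

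- Withdrawal is permitted, not required, and only where the criterion rules out continuing. Nothing says that a facility move prevents a care partner from answering the final survey at Visit 11, which is sent by email or done by telephone or video (section 7.4).
- Section 6.2 already lets the investigator alter the intervention after a significant change without mentioning study withdrawal. A move could be handled there. But 6.2 says nothing about data collection, and neither section refers to the other.
- EHR counts need no contact, and the plan does not say they stop. Since early withdrawals are removed only in the sensitivity analysis, the main analysis evidently keeps them where data exist. This weakens the utilization concern. It does not help the paired tests, which need a second score.
- Early withdrawals are to be telephoned. That shows later contact is thought feasible, but the text does not extend it to the three scales.
- Reasons for withdrawal are recorded, so among 30 dyads the pattern would be visible. Visibility does not recover the missing scores or events.
- Effectiveness is exploratory, the study has one arm and is not formally powered for efficacy, and utilization is only described.

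A reader might go further and infer that follow-up is lost for the dyads who do worst, so that the results are flattered. The documents do not support that. They give no care-partner scores and no acute-visit rates after placement, and a benefit described as later placement says nothing about mood, burden or stress once placement has happened.

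**Conclusion.** The point holds as a gap in the withdrawal rule. A stated, discretionary rule permits loss related to outcome, safety recording stops with it, and the plan provides for no second questionnaire afterwards. The plan is silent, not restrictive, on EHR extraction.

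The documents establish neither the direction nor the size of any bias. The figures above rest on an assumed number of placements and assumed differences after placement; on CES-D-10, 1 to 6 losses and differences of 2 to 8 points give shifts of 0.07 to 1.60 points in either direction. The consequences are confined to the exploratory Aim 2 results, the questionnaire response rates and safety capture. The main progression criterion is not inflated. The change is worth making because it is cheap and because scores and events not collected at the time may not be recoverable.

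**What to change.** In section 5.6, with a cross-reference to 6.2, state that a move to a nursing home, long-term care or assisted living after enrolment does not by itself end study follow-up. Unless consent is withdrawn, continue:

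- the second CES-D-10, ZBI-12 and PSS, by email or telephone;
- AE/SAE recording;
- EHR utilization through the planned window.

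Record placement and its date. Leave the decision on when sessions stop to the existing rules. Limit the provision to the facility criterion; do not extend it to the HP exclusion list, which the documents do not define and which might restrict use of records.

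The cost is protocol wording, plus one survey per affected care partner (the baseline survey visit with the same three scales is listed at 15 to 30 minutes) and continued safety recording; the EHR counts need no contact. The downside is that data after placement describe a different care setting, so they should be flagged in the summaries.

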10.1.8 PROTOCOL DEVIATIONS

This protocol defines a protocol deviation as any noncompliance with the study protocol. The noncompliance may be either on the part of the participant, the investigator, or the study site staff. As a result of deviations, corrective actions will be developed by the site and implemented promptly.

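### Undefined procedure non-compliance can end a dyad's study follow-up, so the second questionnaire and the paired pre-post tests may selectively lose poorly adherent care partners

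*Combined protocol and SAP*

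**What the plan says.** Section 4.1 describes Aim 1 as "the assessment of registration, enrollment, retention, and adherence/fidelity to the program". The counts table in 9.1 turns this into rates:

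- recruitment, a/N
- participation, b/N
- completion (seven or more visits), c/b, and also c/N
- session-specific completion, dk/b
- questionnaire response, em/a and/or em/b

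The completion row reads "Completion rate: c/b, used as main progression criteria". No numerical threshold is given.

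Section 5.6.1 begins "An investigator may withdraw a participant from the study if", and one listed ground is "Significant study procedure non-compliance". The word significant is not defined there or elsewhere. Section 10.1.8 says of deviations that "The noncompliance may be either on the part of the participant, the investigator, or the study site staff", but sets no level at which they matter for withdrawal. After a missed visit, 5.6.2 has staff try to reschedule and "ascertain if the participant wishes to and/or should continue in the study". It also has the reason for withdrawal recorded on the eCRF.

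The three scales are collected at Visit 2 and again only at Visit 11 (7.2, 7.4). Section 9.1 compares them by paired t-tests. A sensitivity analysis then removes those who did not complete the intervention.

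**The concern.** Non-adherence is something this pilot sets out to observe, yet an undefined degree of it can also end observation. The ground is withdrawal from the study, not only from the program, and no section provides for the exit scales afterwards.

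Two results are exposed. The second-questionnaire rate would mix care partners who did not answer with care partners who were no longer asked. The paired comparison would lose poorly adherent care partners in particular. Because 9.1 removes non-completers only in the sensitivity analysis, the main analysis is evidently meant to keep those who have both scores. If non-completers are withdrawn before Visit 11, the main analysis moves toward the sensitivity analysis and the contrast between the two loses its purpose.

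The counts table does not distinguish dyads who stopped from dyads who were stopped, and that distinction matters when refining the program for a larger study.

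**Working it through.** **Inputs.** Up to 30 dyads; a 20% dropout scenario, N = 24; CES-D-10 SD 4; 80% power; two-sided alpha 0.05 (all 9.2). Rates and denominators are from the counts table in 9.1. The number of dyads withdrawn on this ground, k, is not in the documents; k = 0 to 3 is my assumption.

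**1. The plan's own figure.** Solving the paired t-test (noncentral t) for the detectable change gives, for N = 30 and N = 24:

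| SD | N = 30 | N = 24 |
|---|---|---|
| 2 | 1.06 | 1.19 |
| 4 | 2.12 | 2.39 |
| 6 | 3.18 | 3.58 |

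All six agree with Table 3 in 9.2 after rounding.

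**2. Questionnaire 2 response, e2/a or e2/b.** Each withdrawn care partner who would have answered lowers the rate by 1/denominator: 1/30 = 3.3 points, or 1/24 = 4.2 points if only 24 start and b is used. For k = 3 at 30, an illustrative 27/30 = 90% becomes 24/30 = 80%. A care partner who would not have answered anyway changes nothing, so these are upper limits.

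**3. Completion, c/b.** The non-optional intervention visits are Visits 3 to 9, which is seven, and completion needs seven. A dyad that misses one for good reaches seven only if optional Visit 10 or an ad hoc visit counts. A dyad whose visits are late but rescheduled can also still reach seven. Only such dyads can move c/b. If all 30 start and 24 would complete (an assumption), c/b is 24/30 = 80.0% (exact 95% CI 61.4 to 92.3). Withdrawing k would-be completers gives 23/30 = 76.7%, 22/30 = 73.3% and 21/30 = 70.0% for k = 1, 2, 3. Withdrawing dyads that would not have completed leaves 80.0%. The table keeps every starter in b, so the error can only be downward.

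**4. Other rates.** a/N is fixed at consent. b/N changes only if withdrawal falls between consent and the first session. Each later dk/b falls by up to 1/b per withdrawn dyad.

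**5. Paired analysis.** If k of n pairs are lost, the mean change among those retained differs from the mean over all n by (k/n) × D, where D is the retained mean change minus the lost mean change. With k = 3 and n = 30 this is 0.10 × D. If D were 2 CES-D-10 points in size (an assumption that borrows the plan's target change), the shift is 0.2 points.

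**6. Precision.** With 27 pairs the detectable change at SD 4 is 2.24, against 2.12 with 30. That is smaller than the plan's own dropout allowance (2.4 at N = 24).

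**The case against.** The case against is substantial, and most of it stands.

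- A reader might infer that the completion rate, and so the progression decision, is compromised or inflated. The documents do not support this. Withdrawn starters remain in b, most seriously non-compliant dyads would not have reached seven visits anyway, and with no threshold stated a changed decision cannot be shown.
- A reader might infer that feedback from poorly engaged dyads is lost. Section 9.1 assesses acceptability through the post-intervention interview and says it will be sought by telephone after early withdrawal, with no exception for investigator-initiated withdrawal. In context that sentence covers the interview; it does not extend to the three scales.
- A reader might say that the withdrawal ground is the Aim 1 endpoint itself. Study procedures are broader than program attendance, so the two overlap but are not identical. The deviations section leads to corrective action, not withdrawal.
- Safety recording runs "until that person either withdraws or completes study, AEs and SAEs will be recorded". That applies to every withdrawal and is not a defect of this ground. Nothing says that EHR extraction stops.
- The clause is permissive, staff must first try to re-engage the dyad, and the eCRF reason allows the two kinds of withdrawal to be separated. The counts table is offered as an example, so reporting by initiator is not ruled out. It is also not committed to.

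The missing definition, the lost exit scales and the unreported initiator survive these points.

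**Conclusion.** The point holds in a narrow form. Discretionary withdrawal for undefined non-compliance can remove Visit 11 scale data and later session counts from the dyads whose adherence the pilot most needs to see. The size is at most 3.3 points on the Questionnaire 2 rate per dyad at 30 (4.2 with b = 24), plus a selective loss in the paired tests of (k/n) × D, whose direction and size cannot be known in advance. Both rest on an assumed k and on withdrawal from the study meaning that the exit scales are not attempted, which is the natural reading. The power effect is minor. This is a cheap improvement. It does not show that the feasibility rates are uninterpretable or that the withdrawal ground must be struck out.

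**What to change.** 1. In 5.6.1, state that missed visits and procedure non-compliance are recorded as Aim 1 outcome data and do not by themselves end study follow-up.
2. Still attempt the Visit 11 CES-D-10, ZBI-12 and PSS for these care partners, alongside the telephone interview already planned, unless the dyad itself withdraws.
3. In the 9.1 counts table, state that such starters stay in b and count as non-completers if they do not meet the completion definition. Report withdrawals by initiator (dyad or investigator), using the eCRF reason.
4. While editing 9.1, reconcile the completion definition (seven or more visits) with the sensitivity rule (fewer than six sessions), which leaves a dyad with exactly six neither a completer nor removed on session count.

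Withdrawal in the participant's best interest and decisions about the intervention under 6.2 are unchanged. The cost is amendment wording, a split of one count, and one further contact attempt for a few poorly engaged dyads.
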